- Multi-center, randomized controlled trial. The participating centers are Albany Medical Center, Bellevue Woman's Center at Ellis Hospital, and Golisano Children's Hospital. Each center will obtain approval from that center's own Institutional Review Board. It is anticipated that the study will take 2 years to complete.

[figure not shown]
Patient Enrollment:

- The investigators and/or study coordinator will evaluate all infants admitted to the NICU who are less than 48 hours of life from 27 through 36 completed weeks' gestation with mild-moderate RDS.
- If they meet the pre-defined inclusion criteria and informed consent is obtained, they will be randomized to either the INSURE group or LMA group for the initial surfactant administration. Patients will be block randomized in one of three gestational age groups: 27 0/7 - 28 6/7 weeks, 29 0/7 - 32 6/7 weeks, 33 0/7 - 36 6/7 weeks.
- Randomization process: An anticipated 130 patients will be enrolled in the study. Patients will be randomized into three groups using a blind randomization selection method. After computer-generated block randomization, the 130 numbered cards will be placed in sealed, numbered envelopes, and kept in a NICU nurse practitioner office. Each card will indicate LMA or INSURE group and include an identifier code number. After obtaining the signed consent form, the investigators or coordinator will open the next envelope in the appropriate gestational age block.
- Inclusion Criteria:
 - Gestational age (GA) 27 0/7 weeks to 36 6/7 weeks
 - Age < 48 hours
 - Mild-moderate RDS as defined by an FiO₂ requirement of 0.30 - 0.60 on either CPAP or nasal intermittent positive pressure ventilation (NIPPV) for at least two hours to maintain SpO₂ 90-95%
 - Written consent obtained
- Exclusion Criteria:
 - Prior tracheal intubation

- Prior surfactant therapy
- Evidence of pneumothorax, pneumomediastinum, or pneumopericardium
- $\text{FiO}_2 > 0.60$
- Craniofacial or other airway malformation
- Major congenital malformation (cardiac and thoracic defects)
- Apgar score of ≤ 3 at 5 minutes of life or evidence of encephalopathy
- Weight less than 800 grams

Study/Intervention:

The diagram below is a graphic depiction of the study protocol. Criteria for assisted ventilation and other respiratory support will be the same for both groups.

• **INSURE (control group): Atropine + remifentanil + intubation (ETT) + Infasurf**

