The sample size was estimated based on results from the recent study on this population, at the Albany Medical Center NICU. We will thus expect that 30% of the LMA group will meet failure criteria, i.e., the LMA success rate in avoiding later intubation and ventilation will be 70%. For a non-inferiority design, with a clinically relevant non-inferiority margin of 20%, a sample of 130 patients (65 per group) will be needed to conclude non-inferiority of the LMA method compared to INSURE (calculated using a one-sided $\alpha=0.05$, β error=0.20).

➤ Secondary outcome measures:

Groups will be analyzed for secondary outcome differences using chi-square statistics for categorical data, and t-test or non-parametric tests for continuous data, as appropriate for the distribution obtained. The FiO_2 response to surfactant treatment strategies will be compared from baseline to 1 and 8 hours using repeated measures ANOVA and post-hoc Dunnett's test. Time to wean off respiratory support will be compared between groups using Kaplan-Meier analysis, with censoring at discharge.

➤ Interim Analyses:

Reports for the IRB will be prepared after one year of initiation of the trial or enrollment of 50 patients, whichever comes first. Data on the primary outcome, mortality, and major adverse events on the first 50 patients, will be submitted to [name] for purposes of safety monitoring. A difference in primary outcome at the $p<0.01$ level, or a consistent trend towards differences in major adverse events will constitute criteria for recommending that the study be stopped.

E. Risks

- Risk category: Greater than minimal.

This study is considered as a greater than minimal risk study. The study design includes a decreased use of laryngoscopy for tracheal intubation, which is currently the standard method of surfactant delivery. Laryngoscopy is associated with apnea, minor abnormalities in cardiac rhythm, obstructed respiration, increase in systolic blood pressure, decreased heart rate and transcutaneous oxygen tension in preterm neonates during the laryngoscopy (Carbajal, 2007)

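### The plan prepares exactly 130 allocation cards for 130 infants but draws them from three separate gestational-age sequences, with no surplus and no rule for a sequence that runs out

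*Combined protocol and SAP*

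**What the plan says.** The allocation procedure is in the combined protocol and SAP, under Study Design/Subject Population, Patient Enrollment.

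- Target: "An anticipated 130 patients will be enrolled in the study".
- Strata: block randomisation is done within three gestational-age groups (27 to 28, 29 to 32 and 33 to 36 completed weeks).
- Cards: after a computer-generated block randomisation, "the 130 numbered cards will be placed in sealed, numbered envelopes, and kept in a NICU nurse practitioner office".
- Draw: once consent is signed, the investigators or coordinator "open the next envelope in the appropriate gestational age block".
- Screening: the team "will evaluate all infants admitted to the NICU who are less than 48 hours of life" and who fall in the gestational-age range with mild to moderate RDS. The eligibility criteria set no limit per gestational-age group.

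Under Data Analysis, Sample size/Power analysis, "a sample of 130 patients (65 per group) will be needed to conclude non-inferiority". No allowance above 130 is made.

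The document does not give the number of cards per stratum, the block size, the expected gestational-age mix, any spare cards, or what staff do when a stratum has no envelope left.

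**The concern.** A stratified list works as intended when every stratum has more assignments than it can use and the trial stops on the overall total. Here the overall total was used as the number of cards, and the cards were then divided among the strata. Once one group's envelopes are used up, the next eligible infant in that group cannot be randomised by the written procedure, although the trial is still short of 130 and other groups still have cards.

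The team then has three courses, none of them described:

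- Close that stratum and wait for the others. The card split then acts as a gestational-age quota that the eligibility criteria do not mention, and accrual slows.
- Stop short of 130, at some cost in power.
- Improvise, by printing more cards or using another group's envelope, in a trial where the treating team can see the airway assigned.

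**Working it through.** **Inputs from the document.** Planned enrolment 130; cards 130; strata 3; draw within the infant's own stratum; success 70% in the LMA arm (30% failure expected); margin 20 percentage points; one-sided alpha 0.05; power 80%.

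**Assumptions.** INSURE success is also 70% (the plan gives only the LMA rate). The gestational-age mix of eligible infants and the split of cards among strata are not stated, so several are tried.

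**1. The plan's own figure.** n per arm = (z₀.₉₅ + z₀.₈₀)² × 2 × p(1 − p) / margin² = (1.645 + 0.842)² × 2 × 0.70 × 0.30 / 0.20² ≈ 64.9, rounded up to 65 per arm and 130 in total. This reproduces the plan. The sample size is not in question.

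**2. Chance that 130 cards serve the first 130 infants.** Let the cards be split (c₁, c₂, c₃) with c₁ + c₂ + c₃ = 130, and let the infants arrive with shares (p₁, p₂, p₃). The two totals are equal, so no stratum overflows only if every stratum count equals its card count:

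P = 130! / (c₁! c₂! c₃!) × p₁^c₁ × p₂^c₂ × p₃^c₃

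Taking the split that maximises P for each mix, which amounts to a perfect forecast:

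| Assumed mix (27–28 / 29–32 / 33–36 weeks) | Best split | P(exact fit) |
|---|---|---|
| 1/3, 1/3, 1/3 | 44/43/43 | 0.63% |
| 20/40/40% | 26/52/52 | 0.68% |
| 20/30/50% | 26/39/65 | 0.70% |
| 10/30/60% | 13/39/78 | 0.90% |
| 10/10/80% | 13/13/104 | 1.35% |

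So at least one of the first 130 infants finds no card with probability about 98.6% to 99.4%, whichever of these mixes is true.

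**3. How many infants are affected.** The number without a card among the first 130 is the sum over strata of max(Xᵢ − cᵢ, 0). Under a 20/40/40 mix the expected counts are 26, 52 and 52, with standard deviations √(130 × 0.2 × 0.8) = 4.56 and √(130 × 0.4 × 0.6) = 5.59 (twice).

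- Matched split 26/52/52: by the normal approximation, 0.399 × (4.56 + 5.59 + 5.59) ≈ 6.3. Simulation gives a mean of about 6 (5th to 95th percentile 2 to 12).
- Near-equal split 43/43/44: the two larger strata overflow by about (52 − 43) + (52 − 44) = 17. Simulation gives about 17.

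**4. When it happens, and how many must present (simulation, 20/40/40 mix).**

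| Card split | First infant without a card (mean) | Infants who must present to use all 130 cards (mean) |
|---|---|---|
| 26/52/52 | about the 116th | about 148 |
| 43/43/44 | about the 102nd | about 215 |

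The last figure is essentially 43 / 0.20 = 215: the trial waits for the smallest group to use up its 43 cards.

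**5. Power if the trial stops short.** Power = Φ(0.20 / √(2 × 0.21 / n) − 1.645), with n per arm and 70% success in both arms.

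- 130 infants (n = 65): Φ(2.488 − 1.645) = 80%.
- 124 infants (n = 62; 130 less about 6): Φ(2.430 − 1.645) = 78%.

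**6. List length needed.** With 130 cards per stratum (390 envelopes) no list can run out before 130 are enrolled. With 80 per stratum (240 envelopes) the chance of reaching 130 is at least 99.7% under the mixes 1/3 each, 20/40/40 and 20/30/50. With 66 per stratum it falls to about 60% under 20/30/50.

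**The case against.** The strongest reply is that the enrolment paragraph is a short operational summary in which 130 merely restates the target. It calls enrolment anticipated, gives no cards per stratum, and does not forbid a further list. On that reading the gap is one of reporting. This stands in part: exhaustion is about 99% likely rather than certain, and a later list would resolve it. But the text does fix the number of cards, and a single shared sequence of 130 does not fit the instruction to draw within the infant's gestational-age group. How a list is to be extended should be settled before the trial starts.

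A second reply is that each stratum could simply close when its envelopes are used. The procedure then runs to 130 and allocation stays sound. This is right, but it means gestational-age quotas that the plan does not declare, and eligible infants turned away.

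A third reply is that the magnitudes rest on invented inputs. The 148 and 215 do depend on an assumed mix and assumed card splits. The roughly 1% chance of an exact fit barely depends on the mix, but it measures how surely the problem arises, not how much harm it does. The counts of 6 to 17 infants are the better guide to size.

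Two stronger inferences are tempting, and the documents support neither.

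- A reader might infer that allocation concealment is broken. The document describes no borrowing between strata, and a sealed envelope from another stratum is still sealed. Concealment would suffer only if staff could choose which sequence to draw from or deduce the remaining cards.
- A reader might infer that the 30% planning rate no longer applies because the gestational-age mix shifts, the more so as prophylactic caffeine is described only for the two lower groups. The document gives no failure rate by gestational age and no case mix for the earlier trial behind that rate, so no shift can be shown.

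**Conclusion.** The point holds as a flaw in the written allocation procedure: 130 stratum-bound cards cannot be expected to serve 130 infants. For every mix examined, the chance that they do is about 1% even with the best possible card split. Under an assumed 20/40/40 mix, about 6 to 17 of the first 130 eligible infants would have no card, for the matched and near-equal splits respectively.

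The consequences are modest. They are unplanned quotas and slower accrual, a loss of about 2 points of power if the trial stops at 124 (assuming 70% success in both arms), or ad hoc allocation late in an unblinded trial. Closing a full stratum changes the case mix of both arms alike, so the comparison is not biased by that alone. The target of 65 per arm is unaffected. The change should be made because the problem is nearly sure to arise and costs almost nothing to prevent.

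**What to change.** Generate a separate list for each gestational-age group, in whole blocks and longer than that group can need; at least 130 cards per stratum always suffices. Stop enrolment when the total across the three groups reaches 130. State that no card is ever taken from another stratum.

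The cost is a longer computer-generated list and up to about 390 envelopes instead of 130. Each stratum may end with one incomplete block, so the arms may differ slightly from 65/65. Sample size, endpoint and analysis do not change.

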- The neonates randomized to standard management will be given premedication with atropine (0.1 mg/kg) and remifentanil (2 mcg/kg) for endotracheal intubation according to the new standard AMC premedication order sheet.
- A CO₂ detector will be used to verify endotracheal intubation
- Surfactant (Infasurf) therapy will be delivered via ETT, at a dose of 3mL/kg, in 2 aliquots. Surfactant is drawn up in a syringe with a Luer adaptor.
- This is followed by positive pressure ventilation (PPV) for a minimum of 5 minutes before extubation to nasal CPAP (if possible) by 15 minutes after completion of surfactant therapy.
- However, the baby will remain intubated and continue to mechanical ventilation via ETT if one or more of the following occurs:
 - Persistent apnea
 - If this is thought to be related to sedative medication, a one-time dose of naloxone (0.1 mg/kg) may be administered as part of the study protocol
 - Severe retractions (as judged by an attending neonatologist or fellow)
 - Inability to wean FiO₂ < 0.60 to maintain target SpO₂ 90-95%
- Management of RDS, mechanical ventilation, concurrent neonatal issues, and any complications that may arise will be at the discretion of the clinical care team.

• **LMA group: Atropine + LMA + Infasurf**

- The neonates randomized to LMA management will be given atropine (0.1 mg/kg) before the insertion of the size 1 classic LMA. The LMA cuff will be inflated with 2-4 mL of air.
- A CO₂ detector will be used to verify the placement of the device.
- Adequate PPV will be verified by observing adequate chest movements and SpO₂ for at least 1 minute.
- The tip of a T-connector (or, a 5-French catheter) will be cut to reach the distal end of the LMA, to instill a 3 mL/kg dose of Infasurf in 2 aliquots.
- Surfactant will be drawn up in a syringe with a Luer-type adaptor.
- Following surfactant therapy, manual PPV will be provided for a minimum of 5 minutes.

- After spontaneous respirations are judged adequate, the LMA will be removed and nasal CPAP resumed.
- Indications for intubation to initiate assisted ventilation will be one or more of the following:
 - Persistent apnea
 - Severe retractions (as judged by an attending neonatologist or fellow)
 - Inability to wean $\text{FiO}_2 < 0.60$ to maintain target $\text{SpO}_2 90\text{-}95\%$
- Management of RDS, mechanical ventilation, concurrent neonatal issues, and any complications that may arise will be at the discretion of the clinical care team.

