Although the study interventions are limited to the airway used for surfactant administration in the first 1 to 3 days of life, and clinical management or follow-up are not otherwise conditioned by the study, all subjects enrolled will continue in the study up to discharge from AMC, for the purposes of data collection. This will include:

- the FiO₂ and mode of respiratory support before enrollment and at 0, 1, 12, 24, and 48 hours, and 7 and 28 days after initial surfactant administration,
- any need for additional doses of surfactant,
- any need for intubation, and
- any need for mechanical ventilation.

D. Data Analysis

A copy of the data collection sheet that will be used for the study is included.

Primary Outcome Measures: The primary outcome will be success of the surfactant administration strategy in avoiding mechanical ventilation in the first 120 hours of life.

Secondary Outcome Measures:

- Number of surfactant doses
- Days on assisted ventilation
- Day on any noninvasive respiratory support (CPAP/NIPPV modes)
- Days until off respiratory support (supplemental oxygen and/or pressure support)
- Rate pneumothorax and/or pneumomediastinum
- Rate of BPD as defined by oxygen dependence at later of 28 days or 36 weeks' postmenstrual age
- Complications during insertion of LMA or ETT
- Mortality rate

Planned post-hoc analyses include timing of failure by treatment group, which should illuminate the mechanisms of failure by treatment strategy.

➤ Baseline comparability:

Baseline differences between ETT group and LMA group will be compared using t-tests for continuous variables (birth weight, gestational age, age and FiO₂ at enrollment) and chi-square test for categorical variables (race, sex, prenatal care, antenatal steroids, mode of delivery, multiple gestation)

➤ Primary outcome measure:

Our primary outcome for the study is the proportion of infants that will reach the early and/or late failure criteria. The incidence of the failure criteria will be compared using chi-square statistics.

➤ Sample size/Power analysis:

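### Infants are randomised in blocks by gestational age at three hospitals, but the primary comparison ignores both gestational-age stratum and centre, and the route to an allocation at each hospital is not described

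*Combined protocol and SAP*

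**What the plan says.** Section B/C opens with "Multi-center, randomized controlled trial. The participating centers are Albany Medical Center, Bellevue" and goes on to name two further hospitals, each with its own ethics approval. Under Patient Enrollment, "Patients will be block randomized in one of three gestational age groups". For the envelopes, "the 130 numbered cards will be placed in sealed, numbered envelopes, and kept in a NICU nurse practitioner office". After consent, "the investigators or coordinator will open the next envelope in the appropriate gestational age block". The hospital that houses this office is not named. No list or envelope set per centre is described, and no telephone or web route.

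Under Primary outcome measure in section D, "The incidence of the failure criteria will be compared using chi-square statistics". No stratification or adjustment is mentioned. The Baseline comparability paragraph includes gestational age but not centre. The sample-size paragraph states that "a sample of 130 patients (65 per group) will be needed to conclude non-inferiority".

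**The concern.** There are two gaps, one in the analysis and one in the description of allocation.

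**Analysis.** Blocking within gestational-age groups removes between-group variation from the treatment comparison. An analysis that ignores the groups does not use that gain, so its standard error is too large whenever gestational age predicts failure. In a non-inferiority trial this makes the confidence limit a little too wide and the test a little conservative.

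Centre appears in neither the randomisation nor the analysis, although it could plausibly predict failure. One ground for ventilation is "Severe retractions (as judged by an attending neonatologist or fellow", staff can see which device is used, and the surfactant procedures are described as already standardised in one hospital's unit. A chance excess of one arm at a hospital that intubates more readily would then be read as part of the treatment effect.

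**Allocation.** The cards equal the whole planned sample, are held in one office, and are drawn in order. Infants must be under 48 hours old. The text does not say how staff at a hospital without the envelopes obtain the next one, or how the order is kept across sites.

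**Working it through.** **1. The plan's own figure.** Inputs from Sample size/Power analysis: "expect that 30% of the LMA group will meet failure criteria", margin 20 points, one-sided alpha 0.05, power 80%. The INSURE rate is not stated and is taken as equal.

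n per arm = (1.645 + 0.842)² × (0.30×0.70 + 0.30×0.70) / 0.20² = 6.183 × 0.42 / 0.04 = 64.9, so 65 per arm and 130 in total. This reproduces the plan. The standard error of the risk difference at 65 per arm is √(0.42/65) = 0.080, or 8.0 points. Nothing below changes the 130.

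**2. Ignoring the gestational-age strata.** The plan gives neither the gestational-age mix nor failure by group. Assume shares of 25/40/35% from the youngest to the oldest group. The unstratified analysis uses the variance p(1−p) at the average rate p. Under blocking, the estimate varies according to the share-weighted within-group variance. In each case SE = √(2 × variance / 65).

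| Assumed failure by group | Average p | p(1−p) | Within-group variance | SE reported | True SE |
|---|---|---|---|---|---|
| 40/30/20% | 0.290 | 0.2059 | 0.2000 | 0.0796 | 0.0784 |
| 50/30/15% | 0.2975 | 0.2090 | 0.1911 | 0.0802 | 0.0767 |
| 60/30/10% | 0.305 | 0.2120 | 0.1755 | 0.0808 | 0.0735 |

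For the middle row, within-group variance = 0.25×0.25 + 0.40×0.21 + 0.35×0.1275 = 0.1911.

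Power with equal true rates is Φ[(0.20 − 1.645 × SE used) / true SE]:

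- 40/30/20%: 81.1% unstratified, 81.8% stratified.
- 50/30/15%: 81.3% and 83.2%.
- 60/30/10%: 81.9% and 85.9%.

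Simulated trials, which allow for small strata, give a little less than this normal approximation. I put the gain at about 1 to 4 points in the two steeper cases, with nothing to speak of at 40/30/20%.

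**3. Chance imbalance by centre.** Centre shares, centre failure rates and block size are not given. By hand: suppose one centre's failure rate is 20 points from the rest and its arms differ by 6 infants. The risk difference then shifts by 6/65 × 0.20 = 0.018, or 1.8 points.

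By simulation (4,000 trials of 130 infants per scenario; blocks of 4 within three gestational-age groups mixed 20/40/40%):

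| Centre shares | Centre failure rates | Mean shift | 95th percentile of absolute shift | Type I error at margin | Power |
|---|---|---|---|---|---|
| 60/20/20% | 30/20/40% | about 0 | 2.2 points | 0.044 | 0.82 |
| Equal thirds | 30/20/40% | about 0 | 2.8 points | 0.049 | 0.81 |
| Equal thirds | 30/15/45% | about 0 | 4.2 points | 0.048 | 0.81 |

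With centre added to the strata, the 95th percentile falls to about 0.6 to 1.0 point. Type I error (0.04 to 0.05) and power (0.80 to 0.81) are essentially unchanged.

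**4. What stratifying by centre would buy and cost.** With shares of 60/20/20% or equal thirds and a 25/40/35% gestational-age mix, each centre has a 23% to 34% chance of an arm difference of 6 or more under the current scheme. With nine strata and blocks of 4 that chance is below 0.1%, but this threshold flatters the scheme: three groups per centre, each out by at most 2, cannot exceed 6. The price is overall balance. The SD of the total arm difference rises from about 1.6 infants to about 2.7 with blocks of 4, and to about 3.0 with blocks of 4 and 6. At 60/20/20% the smallest cells expect 130 × 0.20 × 0.25 = 6.5 infants, not far above one block.

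**5. Number of envelopes.** Even if the 130 cards were divided in the true 25/40/35% proportions, at least one group would run out before infant 130 in about 99% of simulated trials, with an average shortfall of about 6 cards. The plan does not say what happens then.

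**The case against.** The strongest reply is that randomisation protects the comparison without centre. The estimate is unbiased on average, and leaving centre out of the strata does not invalidate it. The centre effect is an assumption too: the intubation and failure criteria are written out and not limited to one hospital, and no centre failure rate is given. All of this stands. It is why the centre part rests on a small and assumed distortion.

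Three stronger readings are tempting, and the documents do not support them.

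- A reader might infer that centre imbalance could decide the non-inferiority result. The calculated shift is about 2 to 3 points (about 4 under the wider assumed spread), against an 8-point standard error and a 20-point margin, and error rates hardly move.
- A reader might infer that staff at two hospitals cannot draw an envelope. The office is not tied to a named hospital, and the text neither provides for nor excludes telephoned allocation or distributed sets. What can be said is that the route is not described.
- A reader might infer that relaying allocations between hospitals weakens concealment. Nothing in the documents shows this, and holding the list away from the recruiting clinician can protect concealment.

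It can also be said that nine strata are a matter of preference. I agree: they trade better centre balance for worse overall balance and, in small cells of an unblinded trial, more predictable assignments.

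**Conclusion.** The point holds as a modest improvement, not as a threat to validity. The firmest part is the mismatch between a randomisation blocked by gestational age and an analysis that ignores it. Correcting it is worth about 1 to 4 points of power if failure falls steeply with gestational age (50/30/15% or 60/30/10% assumed), and almost nothing if the gradient is mild.

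Centre is not balanced by design. With assumed centre failure rates of 20% to 40%, the resulting shift is at most about 3 points at the 95th percentile, and zero on average. The missing allocation route is a gap in description. These sizes depend on assumed shares, rates and block sizes, none of which the documents give.

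**What to change.** **Analysis.** Replace the unstratified chi-square with a risk difference stratified by the three gestational-age groups, for example with Mantel-Haenszel weights n₁n₀/(n₁+n₀) in each group, and compare its one-sided 95% confidence limit with the 20-point margin. Include centre as an adjustment factor or, if cells are sparse, in a prespecified sensitivity analysis. Add centre to the baseline table. This costs a few lines of text and no extra infants. If gestational age does not predict failure, the loss is negligible.

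**Allocation.** State how each hospital obtains the next assignment: either central allocation, or concealed sets per site with varying block sizes. If envelopes are kept, prepare spares in every group and say what happens if a group runs out. The cost is a central service, or printing and custody of envelopes at each site.

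**Optional.** Stratify the randomisation by centre as well, perhaps with fewer gestational-age groups if a site is small. The cost is the looser overall balance shown above (SD about 3.0 infants instead of 1.6 with blocks of 4 and 6). Adjusting for centre in the analysis is a reasonable alternative.

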Since surfactant administration procedures are already standardized in the AMC NICU, babies will have had at least one clinically indicated chest x-ray before the intervention, and a blood gas is obtained 30 to 60 minutes after the treatment, as per the routine surfactant administration protocol. The study does not alter these routine clinical protocols. Similarly, routine monitoring during the instillation of surfactant will continue, including monitoring of pulse rate, SpO_2 , colorimetric CO_2 exhalation, chest wall rise and auscultation as indicated, in all subjects.

Babies at risk for apnea of prematurity are routinely treated with caffeine. The two lower gestation age groups in this study will continue to undergo prophylactic caffeine therapy for apnea of prematurity.

Only one routine procedure will be standardized due to the study protocol. Babies with RDS on nasal CPAP all have an indwelling orogastric tube; gastric residuals are aspirated and aspirate volumes are recorded, but not always at consistent time points. For this study, the gastric residual will be suctioned before surfactant therapy in each patient, and also 15 minutes after the treatment. The amount of new gastric residual will be recorded.

Failures:

The criterion for **Early Failure** is the need for mechanical ventilation within 1 hour of surfactant therapy due to either persistent apnea, apnea despite naloxone, severe retractions, or the inability to maintain $\text{FiO}_2 < 0.60$ for target $\text{SpO}_2 90\text{-}95\%$

The criteria for **Late Failure** are one or more of the following:

- a sustained $\text{FiO}_2 > 0.60$ required to maintain target oxygen saturation,
- a second dose of surfactant within 8 hours of the first dose,
- more than 2 doses of surfactant, or
- the need for mechanical ventilation within the first 120 hours of life.

- Re-dosing of surfactant
 - Criteria for re-dosing are defined as $\text{FiO}_2 > 0.60$ or $\text{FiO}_2 > 0.30$ with associated clinical signs of worsening RDS.

- If **re-dosing surfactant before 8 hours** has elapsed from the time of initial administration, the dose will be administered via ETT for all study patients, regardless of the group to which they had been randomized.
- If **re-dosing surfactant more than 8 hours** after the initial dose, patients in the LMA group will have a second dose given via the LMA; any surfactant doses beyond the second will be given via ETT. In the ETT group, all doses are given via the ETT.

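### The 8-hour re-dosing rule lets dose timing decide failure in both arms, but waiting spares intubation only in the LMA arm, and the listed records could not show it

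*Combined protocol and SAP*

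**What the plan says.** Under Failures, Late Failure is any of four events: "a sustained $\text{FiO}_2 > 0.60$ required to maintain target oxygen saturation"; "a second dose of surfactant within 8 hours of the first dose"; more than two doses; or "the need for mechanical ventilation within the first 120 hours of life". These apply to both arms. A single second dose after 8 hours is not on the list.

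Under Re-dosing of surfactant, the trigger is FiO2 above 0.60, or FiO2 above 0.30 "with associated clinical signs of worsening RDS". A re-dose before 8 hours goes by endotracheal tube (ETT) in both arms. After 8 hours, "patients in the LMA group will have a second dose given via the LMA", while the INSURE arm continues to use the ETT for every dose.

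In the LMA group text under Study/Intervention, a list introduced by "Indications for intubation to initiate assisted ventilation will be one or more of the following" includes inability to wean FiO2 below 0.60. It has no stated time limit.

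Section D (Data Analysis) first describes the primary outcome as success in avoiding mechanical ventilation in the first 120 hours of life, then as the proportion reaching the early and/or late failure criteria. The FiO2 time points listed just before Section D are pre-enrollment; 0, 1, 12, 24 and 48 hours; and 7 and 28 days.

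**The concern.** Part of the primary composite records when a clinician acted rather than the state of the infant. Two LMA infants who both meet the re-dosing criteria at 7 hours can be scored differently. One dosed at once is intubated for the dose and is a failure. One dosed just after 8 hours is not intubated for it and need not be a failure. In the INSURE arm the same delay also removes the label, but the tube is used either way. The reason to wait is therefore stronger in one arm.

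No blinding of carers or outcome assessors and no adjudication is described, and the device and re-dosing route reveal the arm. In a non-inferiority comparison, failures scored as successes mainly in the LMA arm would favour the study hypothesis.

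A related problem lies at FiO2 above 0.60, which serves as an intubation indication, a re-dosing criterion and, if sustained, a failure. No duration defines sustained, and the text gives no order between re-dosing and ventilating.

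**Working it through.** **Rules side by side (second dose only, no other failure event)**

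| Time of second dose | LMA arm | INSURE arm |
|---|---|---|
| Before 8 h | ETT; failure | ETT; failure |
| After 8 h | LMA; not a failure in itself | ETT; not a failure in itself |

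Crossing 8 hours changes the label in both columns and the route in only one. Exactly 8 hours is not clearly assigned, since the text uses within, before and more than 8 hours.

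**Can the data show when criteria were met?** The listed schedule has no FiO2 record between 1 and 12 hours. The Secondary outcome measures paragraph nevertheless plans an FiO2 comparison at 8 hours. The data collection sheet is mentioned but not reproduced in the text, so it may capture more.

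**The plan's own sample size.** Inputs from Sample size/Power analysis: 30% failure in the LMA arm, margin 0.20, one-sided alpha 0.05, power 0.80. The INSURE rate is not stated; equality at 30% is assumed.

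n per arm = (1.645 + 0.842)² × (0.3×0.7 + 0.3×0.7) / 0.20² = 64.9, rounded up to 65; total 130. The stated figure reproduces.

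**Sensitivity to relabelling.** Assumptions: 65 per arm; true failure 50% (LMA) versus 30% (INSURE), which is the margin boundary; non-inferiority claimed if the upper one-sided 95% Wald limit, d + 1.645 × SE, is below 0.20, where d is LMA minus INSURE failure and SE² = pL(1−pL)/65 + pC(1−pC)/65. The chance of a claim is summed over all pairs of binomial counts. One infant is 1/65 = 1.5 points. With k LMA infants relabelled on average, the LMA rate becomes 0.50 − k/65. For the INSURE arm there are three cases:

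- LMA only: INSURE stays at 0.30.
- Same share of failures: the share is (k/65)/0.50, and INSURE becomes 0.30 × (1 − share). For k = 5 the share is 15.4% and INSURE is 0.254.
- Equal numbers: INSURE becomes 0.30 − k/65.

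| k | LMA only | Same share in both arms | Equal numbers in both arms |
|---|---|---|---|
| 0 | 4.6% | 4.6% | 4.6% |
| 1 | 6.7% | 5.5% | 4.7% |
| 3 | 13.3% | 7.6% | 5.0% |
| 5 | 23.3% | 10.4% | 5.1% |

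**How close one infant can be.** With 20/65 INSURE failures, 24/65 LMA failures gives 0.0615 + 1.645 × 0.0828 = 0.198 and passes; 25/65 gives 0.0769 + 1.645 × 0.0832 = 0.214 and does not.

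**The case against.** The strongest reply is that the 8-hour failure item is the same in both arms, so delay relabels INSURE infants too. If equal numbers move, the error rate hardly changes, and INSURE-only moves would lower it below 4.6%. This stands. A reader might infer that the rules bias the trial toward non-inferiority. The documents do not support that: they show a difference in incentive and no evidence that anyone would act on it.

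Second, a reader might infer that an infant unchanged since entry already qualifies for re-dosing, because entry is at FiO2 0.30 to 0.60. That is too strong, because the lower trigger also requires worsening signs. What remains is that those signs are a bedside judgement.

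Third, a reader might see a flat contradiction over FiO2 above 0.60. The LMA intubation list directly follows removal of the device, and Early Failure within 1 hour repeats much the same reasons, so the list can be read as peri-procedural. The protocol diagram, which is not shown in the text, may give an order. The overlap is therefore an ambiguity to reconcile rather than a proven conflict.

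Fourth, several safeguards exist. Sustained FiO2 above 0.60, a third dose, and ventilation within 120 hours of life are failures whatever the re-dose timing, and support criteria are stated to be common to both groups. These limit the problem to a subset of infants. They do not cover the re-dosing route, and sustained is undefined.

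Finally, under the narrower wording of the primary outcome (avoiding mechanical ventilation) the re-dosing item would not enter. It matters under the composite, which is what the primary analysis paragraph specifies.

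**Conclusion.** The concern holds in limited form. Timing of a second dose around 8 hours can move infants across the primary composite in either arm, the reason to wait is stronger in the LMA arm, and the listed FiO2 schedule could not show whether this happened. Neither the direction nor the size of bias can be established from the documents. The 23.3% figure is a worst case that assumes five infants relabelled in one arm only. The same-share case reaches 10.4%, and the equal-numbers case is essentially harmless. All figures also assume a Wald bound and true rates at the margin.

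The point justifies better recording, one pre-specified sensitivity analysis and clearer definitions. It does not justify replacing the primary component: scoring every moment at which the criteria are met would count brief FiO2 excursions as failures, and would still rest on unblinded judgement.

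**What to change.** Keep the primary component as written, and:

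1. Record prospectively, in both arms, the time at which re-dosing criteria are first met.
2. Pre-specify a sensitivity analysis of the primary outcome that scores failure when those criteria are met within 8 hours of the first dose, whether or when a dose is given. Apply to FiO2 above 0.60 the same minimum duration as in item 3, so that brief excursions do not count.
3. State one duration for sustained FiO2 above 0.60 for endpoint scoring, identical in both arms.
4. Reconcile the LMA intubation list with the Failures and Re-dosing text on FiO2 above 0.60 after 8 hours in the LMA arm. The clinical rule is for the investigators to choose.

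Cost: protocol wording, one added data field and one added analysis. A limit remains, because the onset of worsening would still be judged by unblinded staff. The field has to be in place from the start, since the listed schedule would not recover these times later.
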